- **b.** Marijuana smokers and Marijuana Exposed Healthy Controls (n=20) will be imaged with [¹¹C]carfentanil PET, after overnight abstinence from marijuana smoking. Subjects will smoke a marijuana cigarette before or during the drug condition PET scan.

Aim 3: To examine the magnitude, location and timing of marijuana-induced dynorphin release. Cannabis has diverse effects on the endogenous opioid system. We will image Marijuana Smokers and Marijuana Exposed Healthy Controls (n=20) with [¹¹C]EKAP PET, after overnight abstinence from marijuana smoking. Subjects will smoke a marijuana cigarette before or during the drug condition PET scan.

2. **Background:** Describe the background information that led to the plan for this project. Provide references to support the expectation of obtaining useful scientific data.

Page 9 of 51

The neurochemistry of drug addiction. Drug addiction is a widespread public health issue, affecting at least one quarter of the adult U.S. population. A key process of chronic drug use is the transition from voluntary to compulsive use in spite of adverse consequences. The rewarding aspects of drug abuse are known to be critical to both the initiation, i.e., voluntary, and maintenance of drug use⁴. Reward processes are primarily influenced by the DA and opioid neurotransmitter systems. It has been hypothesized that DA influences reward "wanting", while the opioid system governs reward "liking"², both of which are critical for understanding neurochemical processes underlying compulsive drug use. For example, initial drug seeking for the pleasurable aspects of the drug ("liking") often gives way to habitual drug use ("wanting"), particularly in response to drug cues, despite individuals reporting little pleasure from the drug itself⁵. While much preclinical work has studied dopamine-opioid interactions in reward response^{6,7}, extending this work to study the neurochemistry of reward response in *clinical* substance abuse disorders has been limited.

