Aim 3: To examine the magnitude, location and timing of marijuana-induced dynorphin release. Cannabis has diverse effects on the endogenous opioid system. We will image Marijuana Smokers and Marijuana Exposed Healthy Controls (n=20) with [¹¹C]EKAP PET, after overnight abstinence from marijuana smoking. Subjects will smoke a marijuana cigarette before or during the drug condition PET scan. For Aim 1 using a single scan paradigm, drugs will be administered beginning approximately 35 minutes after the radiotracer injection, as previously validated³⁵. For Aim 2 and 3, since this approach has not yet been done in people with [¹¹C]carfentanil or [¹¹C]EKAP, we will use a two scan paradigm (baseline and challenge). Drugs will be administered either before (approximately 15 min prior to radiotracer injection) or during (30-60 minutes after radiotracer injection) drug condition PET scan, which may occur after a baseline condition PET scan. The scans will be analyzed to produce the magnitude *and* temporal characteristics of the DA and beta-endorphin signature of drug use under each condition.

3.2 Subject Selection:

All research subjects will be recruited under guidelines of the Yale University Institutional Review Board (Human Investigation Committee). Subjects will be recruited from the community at large via IRB-approved advertising (television, newspaper, postings in community locations, Craigslist, Facebook).

Screening Evaluation

Potentially eligible subjects will undergo an initial screening evaluation within 6 months of PET scanning. The purpose of this evaluation is to ensure that subjects meet study criteria. After informed consent is obtained, a medical history, vital signs, physical examination, and EKG will be performed. Several laboratory tests will be performed at this visit, which may include a complete blood count (CBC), chemistry profile, thyroid function studies, serum ß-HCG (women only), urinalysis, and urine toxicology screen. All female subjects will undergo a pregnancy test at the time of screening. Additionally, urine pregnancy tests will be done on the day of each PET scan before radiotracer injection. Urine drug screens will be done at intake and on PET days.

3.3 Assessments:

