Subjects will have abstained from cannabis use overnight and at least for 12 hours (verified by carbon monoxide levels \leq 11 ppm). At the pre-determined time (approximately 35 minutes following radiotracer injection for [¹¹C]raclopride; from approximately 15 min before radiotracer injection to 60 min afterwards for [¹¹C]carfentanil), subjects will smoke up to the entirety of a standardized cannabis cigarette (Between 3.5% and 10% THC) obtained from NIDA. We will use a protocol similar to other studies in which subjects inhale for 3 sec, hold the smoke in their lungs for 5 sec and exhale. They will smoke up to the entirety of the cigarette at approximately 30 sec intervals per puff, subjects will not be asked to smoke more than they are accustomed to. Subjects will rate their craving immediately before smoking, and their satisfaction from craving, feeling of reward, and drug "liking" periodically thereafter. Subjects will be asked about unpleasantness and perceived "high" pre- and post-scan.

Data Processing

All PET data will be reconstructed with an iterative reconstruction algorithm, MOLAR, designed specifically for the HRRT. MOLAR incorporates attenuation, scatter and deadtime, and subjectmotion (detected by the Vicra system), into the forward projection model for the scanner. Emission images are binned into equal frame times (typically 3 minutes). Following image reconstruction, an early summed image (0-12 min) will be registered to the subject's MR image, which will be registered to an MR template so PET can be transformed to a standard (MNI) space. HYPR filtering will be applied to all emission data before analysis. Ip-ntPET and voxelwise analysis will be conducted.

4. Genetic Testing N/A

A. Describe

i. the types of future research to be conducted using the materials, specifying if immortalization of cell lines, whole exome or genome sequencing, genome wide association studies, or animal studies are planned

- One 10 mL tube of blood will be collected for DNA for testing of polymorphisms in genes of interest to drug addiction. This sample may be collected during the screening appointment or on one of the PET scan days.

Page 19 of 51

ii. the plan for the collection of material or the conditions under which material will be received

-as above, a blood sample will be collected at intake to test polymorphisms of interest for drug dependence.

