Up to 110 subjects (55 men, 55 women) will participate in the study. According to census figures, minority groups comprise approximately 50% of the population of New Haven (36.1% African-American, 13.2% Hispanic, 0.3% Native American, 2.4% Asian, and 4.1% other). While we prefer to have 60 subjects complete both Aim 1 and Aim 2, we anticipate up to a 50% drop out rate between scans so we are allowing for the possibility having 110 subjects participate.

All subjects will be 18-55 years of age and physically healthy. All research subjects will be recruited under guidelines of the Yale University Institutional Review Board (Human Investigation Committee). Subjects will be recruited from the community at large via IRB-approved advertising (television, newspaper, postings in community locations, Craigslist, Facebook). All participants will be screened initially on the telephone by a research assistant who will schedule the initial intake assessment. The screening and scanning sessions will involve psychological tests in the form of rating scales and questionnaires. These are all noninvasive questionnaires, e.g., to assess mood and craving, and should add no risk.

6. **Subject classification:** Check off all classifications of subjects that will be specifically recruited for enrollment in the research project. Will subjects who may require additional safeguards or other considerations be enrolled in the study? If so, identify the population of subjects requiring special safeguards and provide a justification for their involvement.

Children	🔀 Healthy	Fetal material, placenta, or dead fetus
Non-English Speaking	Prisoners	Economically disadvantaged persons
Decisionally Impaired	Employees	Pregnant women and/or fetuses
Yale Students	\boxtimes Females of ch	nildbearing potential

NOTE: Is this research proposal designed to enroll children who are wards of the state as potential subjects? Yes No (If yes, see Instructions section VII #4 for further requirements)

7. Inclusion/Exclusion Criteria: What are the criteria used to determine subject inclusion or exclusion?

Page 21 of 51

General Inclusion Criteria:

- 1. Men and women, aged 18-55 years
- 2. Able to read and write English and give voluntary written informed consent
- 3. Not treatment seeking or using treatment medications

Tobacco Smokers

- 1. Have a Fagerström Test for Nicotine Dependence (FTND) rating of at least 3.
- 2. Have been using at least 7 cigarettes per day for at least 1 year

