- 3. Carbon monoxide levels > 10 ppm during intake evaluation
- 4. Urine cotinine levels of > 150 ng/mL during intake evaluation
- 5. Are not current users of marijuana or other illicit drugs

Marijuana Smokers

- 1. Meet DSM-V criteria for cannabis use disorder based on the structured clinical interview diagnostic (SCID) or regular cannabis use of >5 times/week
- 2. Test positive for THC
- 3. Have been smoking cannabis on a regular basis for \geq 1 year

Marijuana Exposed Health Controls

1. Do not meet DSM-V criteria for cannabis use disorder based on the structural clinical interview diagnostic (SCID)

2. Have used cannabis in the past recreationally

General Exclusion Criteria:

- 1. Current significant medical condition such as neurological, cardiovascular, endocrine, renal, liver, or thyroid pathology.
- 2. History of or current neurological or significant psychiatric disorder such as schizophrenia or bipolar disorder (DSM-IV Axis 1).
- 3. History of significant head trauma.
- 4. Women who are pregnant or nursing, or fail to use one of the following methods of birth control unless she or partner is surgically sterile or she is postmenopausal (hormone contraceptives [oral, implant, injection, patch, or ring], contraceptive sponge, double barrier [diaphragm or condom plus spermicide], or IUD).
- 5. Regular or current significant use of any prescription, herbal or illegal psychotropic medications (e.g., antidepressants, antipsychotics, anxiolytics, ecstasy) in the past 6 mo, with no current illegal drug use confirmed by urine toxicology (marijuana when relevant).
- 6. Significant substance misuse (including alcohol, and excluding cannabis and marijuana when relevant) that in the PI's determination interferes with the study results or safety of the subject.
- 7. Have MRI-incompatible implants and other contraindications for MRI, such as a pacemaker, artificial joints, non-removable body piercings, claustrophobia, etc.
- 8. Subjects with history of prior radiation exposure for research purposes within the past year such that participation in this study would place them over FDA limits for annual radiation exposure. This guideline is an effective dose of 5 rem received per year.

Page 22 of 51

- 9. Subjects with current, past or anticipated exposure to radiation in the work place within one year of proposed research PET scans.
- 10. Subjects with history of IV drug use which would prevent venous access for PET tracer injection.

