The subject's health and safety will always be the primary concern of the doctors and staff performing the study. In the event of an unexpected outcome, all necessary medical action will be taken.

Risks associated with marijuana smoking

3.5%-10% THC is considered a moderate dose that should not lead to any adverse effects in regular cannabis users. Minimization of the risk entailed by cannabis smoking will be accomplished by (a) criteria for a history of recent, regular use of cannabis \geq 5 times/week (b) test positive for THC at screening (c) have been smoking cannabis on a regular basis for \geq 1 year and (d) stringent criteria for the absence of clinically significant medical or primary psychiatric disorders.

Measures of heart rate, systolic blood pressure, and diastolic blood pressure will be obtained at baseline and every 15 minutes after cannabis administration. In the event of psychiatric complications such as psychosis or anxiety, and appropriately trained psychiatric support staff involved in the study will be available and medications to alleviate such conditions (e.g., benzodiazepines) will be on hand.

Page 27 of 51

Risks Associated with Carfentanil

Although Carfentanil can be considered a potent analgesic, side effects from the amount of carfentanil in the tracer dose should be minimal to non-existent. Monitoring of oxygen saturation, blood pressure, pulse, and other vitals are done before, during and for minimum of 30 minutes post scan (2.5hrs post carfentanil). Should the need arise oxygen and naloxone are on hand to reverse any negative side effects that may occur. MD will decide if subject is ready for discharge should there be any clinically significant changes from baseline vitals. Should vitals not return to baseline after additional monitoring and treatment, MD may decide to have subject sent to the ER. In this case a SAE will be filed.

- 11. **Data and Safety Monitoring Plan:** Include an appropriate Data and Safety Monitoring Plan (DSMP) based on the investigator's risk assessment stated below. (Note: the HIC will make the final determination of the risk to subjects.) For more information, see the Instructions, page 24.
 - a. What is the investigator's assessment of the overall risk level for subjects participating in this study?

This study represents a greater than minimal risk to the participants.

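### Three of the four entry safeguards that Section IV.10 relies on for cannabis smoking are not required of Marijuana Exposed Healthy Controls, who have no recency or prior-tolerability floor

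*Combined protocol and SAP*

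**What the plan says.** All references are to the combined protocol and SAP.

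- **Who is challenged.** Section IV.1, Aim 2b: "Marijuana smokers and Marijuana Exposed Healthy Controls (n=20) will be imaged with" carfentanil. Section IV.3.1, Aim 3: "We will image Marijuana Smokers and Marijuana Exposed Healthy Controls (n=20) with" EKAP. In both aims the drug-condition scan includes smoking a marijuana cigarette, and no separate procedure is given for controls.
- **Dose.** Section IV.3.4, Marijuana Smoking in the Scanner: "subjects will smoke up to the entirety of a standardized cannabis cigarette (Between 3.5% and 10% THC) obtained from NIDA". The same paragraph adds a limit: "subjects will not be asked to smoke more than they are accustomed to".
- **Entry criteria for controls.** Section IV.7 has two group-specific items: no cannabis use disorder on structured interview, and "Have used cannabis in the past recreationally". The general criteria also apply, including "Men and women, aged 18-55 years". General exclusion 5 ends "with no current illegal drug use confirmed by urine toxicology (marijuana when relevant", without saying what this means for controls.
- **Stated risk minimisation.** Section IV.10: "Minimization of the risk entailed by cannabis smoking will be accomplished by (a) criteria for a history of recent, regular use of cannabis" (at least five times a week), followed by (b) a THC-positive test at screening, (c) regular smoking for a year or more, and (d) absence of important medical or primary psychiatric disorders.
- **Reassurance on dose.** Sections IV.9 and IV.10 speak of regular users when they say adverse effects are not expected. Section V.A.2 extends the expectation of good tolerability to exposed users.

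**The concern.** Section IV.10 describes entry safeguards as though everyone who smokes cannabis in the study were a current regular user. One dosed group is not, and it is likely to be the group least used to the drug. A reader of Section IV.10 alone, such as an ethics reviewer, would take (a) to (c) as applying to all.

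The stake is subject safety. Section IV.9 lists anxiety, panic, paranoia and, rarely, psychosis, and says these can be very distressing. It also lists tachycardia and blood pressure change. In Aim 3 a radial artery line is in place on the scan day. The same section calls the unpleasant effects rare in the investigators' experience, without saying in which kind of user, and says the physical effects usually settle on their own.

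**Working it through.** The plan states no figure on this point, so the check sets the sections side by side.

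**Step 1: which Section IV.10 safeguards are required by Section IV.7?**

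| Safeguard | Marijuana Smokers | Exposed controls |
|---|---|---|
| (a) recent regular use, at least 5 times/week | Not strictly: a use disorder is accepted instead of use more than 5 times/week | Not required |
| (b) THC-positive | Required | Not required |
| (c) regular smoking for 1 year or more | Required | Not required |
| (d) medical and psychiatric exclusions | Required, through the general exclusions | Required, through the general exclusions |

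Controls: 4 − 3 = 1 of 4. Smokers: 4 − 1 = 3 of 4 strictly, with (a) met by one of two routes. The threshold itself also differs: at least 5 in Section IV.10, more than 5 in Section IV.7.

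**Step 2: what floor do the control criteria set?** Recency: none. Number or frequency of past uses: none. Tolerability of past use: none. The no-use-disorder item limits heavy use and sets no minimum. As a logical extreme only, a 55-year-old who last used cannabis at 18 satisfies the group criteria (55 − 18 = 37 years).

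**Step 3: does general exclusion 5 supply a floor?** It can be read two ways.
- If marijuana is not exempted for controls, they must be THC-negative, the reverse of (b).
- If it is exempted, recent use is allowed but not required.

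Neither reading sets a minimum.

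**Step 4: does the dosing text supply one?** The limit to what the subject is accustomed to is a real protection. It has no unit, and it does not mention strength or time since last use. Strength may vary by a factor of 10 / 3.5 = 2.86, with no rule linking it to group or experience.

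**Step 5: how much exposure?** One drug-condition scan in Aim 2b plus one in Aim 3 gives up to 1 + 1 = 2 planned challenges for a control who takes part in both. The number of controls is not stated: a single n=20 follows the two groups in each aim.

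**Step 6: can excess risk be estimated?** That would need reaction rates by recency or frequency of use. The documents give none. Section IV.9 cites prior THC administration to users and abusers without serious adverse events, but not how recent or frequent their use was.

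**The case against.** The case on the other side is substantial, and much of it stands.

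- **Exposed users were considered.** A reader might infer from Section IV.10 that the sponsor overlooked this group. Section V.A.2 does not support that, since it names exposed users when it says the dose should be well tolerated. That sentence is an expectation, though: it comes with no data for exposed users and no criterion.
- **Controls are not unprotected.** A reader might take 1 of 4 to mean that controls have a quarter of the protection. It is a count of listed items. The accustomed-amount limit, the study physician's decision on participation (Section IV.8), vital signs every 15 minutes, psychiatric support and benzodiazepines all cover them. What stands is that monitoring and treatment act after a reaction begins, and the physician has no written cannabis criterion to apply.
- **Use history is collected.** It would be wrong to say it is merely optional. Section IV.3.3 has drug history taken at intake, and Section IV.9 has participants asked about current or past drug use. The cannabis-specific instruments in Section IV.3.3.c are the optional part. Timeline Followback covers 30 days, and the Marijuana Smoking History Questionnaire is described as covering lifetime and the past 30 days. Whether either dates a remote last use cannot be checked, because the forms are not in the documents.
- **Part of this is drafting.** Safeguard (a) does not strictly bind smokers either, so Section IV.10 is inexact for both groups. That is true, but (b) and (c) still separate the groups.
- **Scan loss.** It is tempting to add that distressed controls will lose their drug-condition scans. The documents do not support much weight on this: stopping early is allowed, head motion is tracked, and on the HRRT it is corrected event by event.

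**Conclusion.** The point holds as a gap between the stated risk minimisation and the entry criteria. Of the four safeguards in Section IV.10, three are not required of exposed controls, and those controls have no floor on recency, amount of past use or past tolerability. This rests on reading Section IV.7 as the complete list of criteria for the group. No unwritten rule appears elsewhere in the document.

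A reader might go further and conclude that controls face a known higher risk, or that each must finish a 10% cigarette. Neither follows. The excess risk cannot be computed from the documents, the unpleasant effects are described as rare, and the amount smoked is capped by what the subject is used to. Confidence is high on the text and does not extend to the size of any harm. The change is worth making because it is a cheap safety gain and because Section IV.10 is at present wrong for one dosed group.

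**What to change.** Before the next exposed control is challenged:

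1. **Section IV.7.** Add for exposed controls a minimum recency and a minimum number of past inhaled uses, and exclude anyone with a past panic, paranoid, psychotic or fainting reaction to cannabis. The sponsor should set and justify the cut-offs; at least one use in the past 12 months is an example, since the documents give no figure. State in exclusion 5 whether controls may be THC-positive. A 12-month window works either way.
2. **Sections IV.3.3.c and IV.3.4.** Make the Marijuana Smoking History Questionnaire and Timeline Followback mandatory for controls at screening, and record the date of last use. Have the study physician set a maximum number of puffs before the scan. Record cigarette strength and puffs taken.
3. **Section IV.10.** State (a) to (c) for Marijuana Smokers only, worded to match Section IV.7 (including the use-disorder alternative), and list the protections that apply to controls.

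A lower strength for controls is optional for the sponsor, since it may reduce the response being measured. Moving smokers to 3.5% is not advised. It would split that group by dose partway through the study and weaken comparability with Aim 1b, for a group this concern does not cover.

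The cost is a protocol amendment and a consent update. Both instruments are already listed, so no visits or scans are added. Some candidate controls become ineligible; how many cannot be derived from the documents.

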3.4 Procedures

Screening, Evaluation and Clinical Ratings

Screening, evaluation and clinical ratings (as described above) are obtained during the screening process.

Magnetic Resonance Imaging (up to 1 hour)

Magnetic resonance imaging (MRI) scans (3T) will be collected in each subject to co-register PET and MRI for image analysis as well as collect resting state data. MRI is without contrast. Within approximately two weeks of the PET study, an MRI will be acquired at the Yale University MRI Center. Subjects will be taken through a ferromagnetic metal detector before entering the scan room.

3T Scan sequence:

Series 1: 3 plane localize Series 2: Sag 3d tfl; 256fov; 1mm thick slices; 176 slices total; TE 2.77; TR 2530; TI 1100; FA 7; 256X256 1 average.

Series 3 – Resting state: Ep2d bold; 210fov; 2.5mm thick slices; TE 30; TR 3400; FA 85; 84x84 (Run twice).

MR images provide a matching anatomical atlas for creating individualized region-of-interest templates for each subject. We will also examine functional connectivity at rest.

If an MR image is already on file at the PET Center, and has been collected within a reasonable time period, a new MRI may not need to be collected.

A member of the research staff will accompany the subject and stay for the duration of the mri.

PET Scans

PET experiments will be conducted at the Yale University PET Center. Subjects will have one [¹¹C]raclopride PET scan, two [¹¹C]carfentanil PET scans, and/or two [¹¹C]EKAP PET scans with different radiotracer studies on separate days. If technical difficulties arise, additional PET scans

Page 16 of 51

may be scheduled at a later date, for a total of up to 8 PET scans. We may ask subjects to refrain from eating 4-6 hours prior to injection and remain fasting until the study is over. Subjects may also be asked to refrain from drinking caffeinated beverages that day, and from drinking alcoholic beverages the week prior to the scan.

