All participating subjects will be asked to abstain from smoking or drug use for approximately 12 hrs before each scan (e.g., overnight abstinence) to maximize craving). Upon arrival at the PET center, subjects will complete questionnaires on drug urges, withdrawal symptoms, and mood. Plasma will be drawn before scans to measure drug levels in the blood. CO levels will also be measured (MicroDirect CO Monitor) upon arrival for scan. CO < 11ppm indicates that subjects were abstinent as requested prior to tobacco and marijuana sessions. If the CO level is positive, subject participation will be up to the discretion of the PI. .Urine drug tests may be performed before all PET scansSubjects' vitals will be monitored throughout the scans up until at least an hour before discharge.

For all women, a urine pregnancy test will be performed at the beginning of the imaging day, prior to radiotracer injection, at the Yale University PET Center.

PET Data Acquisition and Analysis

Subject preparation consists of intravenous (IV) catheterizations and immobilization of the head. Venous catheters will be used for IV administration of the radiotracer and blood sampling. For [¹¹C]EKAP scans, a radial artery catheter will be inserted by an experienced physician in the morning before the PET scan. The site will be anesthetized with lidocaine prior to arterial line insertion. The arterial line will remain in place for the whole day of scanning, after which it will be removed. PET scans are acquired as subjects rest using an HRRT, PET-CT, or NX-CT scanner . For HRRT scans, a transmission scan using an orbiting ¹³⁷Cs point-source is obtained for each emission scan. Motion correction will be performed dynamically with measurements from the Vicra (NDI Systems, Waterloo, Ontario) used by a dedicated list-mode reconstruction algorithm ⁵².

The PET scans will be acquired using IV bolus or bolus plus constant infusion administration of up to 20 mCi or less of high-specific activity [¹¹C]raclopride, and/or[¹¹C]carfentanil, and /or [¹¹C]EKAP using a dynamic PET scan of up to 120 min.

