a. The presence of neurotransmitter activation is determined, statistically, by comparing the best lp-ntPET fit to MRTM. The F-statistic is used to compare formally the residual sum of squares for each model taking into account differences in degrees of freedom. MRTM has 3 parameters. IpntPET has 7 (4 explicit, 3 implicit). Only those voxels for which the F-test indicates an improved fit (p<0.01) are retained for the neurotransmitter movie. The map of all retained voxels is a "Significance Mask".

b. To correct for multiple comparisons (~1000 voxels in our striatal mask) we apply a clustersize threshold to the Significance Mask. For a scan on the HRRT, 15-20mCi dose of radiotracer, and approximately 3 minute time-frames, we have determined that a cluster-size threshold of 17 contiguous voxels is the minimum size activation cluster to retain so that we achieve a global incidence of less than 1/10 subjects with any false positive clusters.

SECTION V: RESEARCH INVOLVING DRUGS, BIOLOGICS, RADIOTRACERS, PLACEBOS AND DEVICES

If this section (or one of its parts, A or B) is not applicable, state N/A and delete the rest of the section.

A. DRUGS, BIOLOGICS and RADIOTRACERS

1. **Identification of Drug, Biologic or Radiotracer:** What is (are) the **name(s)** of the drug(s) biologic(s) or radiotracer(s) being used? Identify whether FDA approval has been granted and for what indication(s).

1. ["C]**Raclopride** (radiotracer for PET studies), IV

[¹¹C]Raclopride is the most commonly used D2/3 radioligand for PET studies in humans. It has been used in many PET centers through out the world and its dosimetry has been well characterized and published. Studies contained in this protocol will not commence until the Yale New Haven Hospital RSC grants approval for this protocol.

An application will be submitted to the Yale New Haven Hospital RSC for use of [¹¹C]raclopride in this protocol as it is covered under IND# 132971. No subjects will be scanned until approval is obtained fro YNHH RSC.

2. ["C]Carfentanil (radiotracer for PET studies), IV

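### Does the 17-voxel cluster threshold, stated only for HRRT striatal scans, leave the other permitted scans without false-positive control?

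*Combined protocol and SAP*

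**What the plan says.** Section IV.12(a) of the combined protocol and SAP detects activation voxel by voxel, "comparing the best lp-ntPET fit to MRTM" with an F-test and keeping voxels at p<0.01. Section IV.12(b) adds the only multiplicity control in the document: "To correct for multiple comparisons (~1000 voxels in our striatal mask) we apply a clustersize threshold to the Significance Mask". The size is then fixed for named conditions: "For a scan on the HRRT, 15-20mCi dose of radiotracer, and approximately 3 minute time-frames, we have determined that a cluster-size threshold of 17". Clusters with fewer adjoining voxels than this are dropped, so that fewer than 1 in 10 subjects have any false cluster.

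The acquisition text in Section IV.3.4 is wider: "PET scans are acquired as subjects rest using an HRRT, PET-CT, or NX-CT scanner". Injected activity there is "up to 20 mCi or less of high-specific activity" tracer. Section IV.3.4, Data Processing, sends all PET data through MOLAR, which it describes as built for the HRRT, with Vicra motion data. It then plans lp-ntPET and voxelwise analysis.

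Section IV.3.1 uses one scan for raclopride. For the opioid tracers it uses a baseline and a challenge scan, "since this approach has not yet been done in people with" carfentanil or EKAP.

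**The concern.** Location of release is part of all three aims, and the cluster rule decides which voxels count as activation. The rule's stated error rate belongs to one scanner, one activity range, one frame length and one mask. A scan on PET-CT or NX-CT has different resolution and noise, so 17 voxels cannot be assumed to give the same rate there. The analyst would have to reuse 17 without a known error rate or pick another size, conceivably after seeing the maps. The opioid scans raise a second question: Section IV.12 mentions neither the two-scan contrast nor any mask outside the striatum. If the gap mattered, a reader could not tell how often a reported cluster was noise, or how often a real one had been discarded.

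**Working it through.** **1. How much rests on the rule.** Inputs from Section IV.12: about 1000 voxels, p<0.01 per voxel. Expected false voxels with no cluster rule, taking the voxel test as exact: 1000 × 0.01 = 10. If the voxels were independent, the chance of at least one is 1 − 0.99^1000 = 0.99996. So control does depend on the cluster rule.

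**2. What the stated rate means.** Below 0.10 per subject, a group of 20 has fewer than 0.10 × 20 = 2 subjects expected to show a false cluster. At exactly 0.10, with independent subjects, the chance that at least one of 20 does is 1 − 0.9^20 = 0.878. This is a per-subject tolerance that the plan states openly for its own conditions.

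**3. Can 17 be reproduced, or a rate worked out elsewhere?** No. Either calculation needs voxel size, smoothness after HYPR filtering, the adjacency rule and the null data used. None is in the document. Nothing confirms or contradicts 17 for the HRRT, and the rate on another scanner could be higher or lower.

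**4. Which planned scans fall outside the conditions.**

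| Condition in IV.12(b) | Rest of the plan | Reading |
|---|---|---|
| HRRT | IV.3.4 also permits PET-CT and NX-CT; Data Processing describes an HRRT-only pipeline; Tobacco Smoking in the Scanner describes clearance to smoke only in the HRRT | A real gap in coverage; the split across scanners is not given |
| 15–20 mCi | IV.3.4 and IV.9 (radiation risks) give a 20 mCi ceiling | A ceiling is not a plan to scan below 15 mCi, and no section plans one |
| About 3-minute frames | Data Processing: typically 3 minutes | Agrees |
| Striatal mask; tracer not named | IV.3.4 names prefrontal cortex and amygdala, but for binding-potential estimates | No contradiction; use on opioid scans not stated |

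**5. Size of the opioid question.** Section IV.1 gives 20 + 20 = 40 raclopride scans, (20 + 20) × 2 = 80 carfentanil scans and 20 × 2 = 40 EKAP scans, 160 in all. This reads each n=20 as the group total, including the combined marijuana and exposed-control group, and leaves out repeats. Opioid scans: 80 + 40 = 120. Half of these, 40 + 20 = 60, are drug-free baselines with no drug response to map. That leaves at most 60 challenge scans. Section IV.3.1 lets the drug be given about 15 minutes before injection or 30–60 minutes after it. The lp-ntPET test looks for a change during the scan, so only the second timing clearly suits it. How many scans will use that timing is unknown, so calling 120 of 160 (75%) uncovered would overstate the point.

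**The case for a change.** The strongest opposing case is that the other scanners are more than a stray mention. Section IV.3.4 gives NX scans their own motion tracking, and gives NX-CT and PET-CT scans a CT for attenuation correction. Clearance to smoke in the HRRT is described but not required, and smoking may precede an opioid challenge scan. The Background section speaks of validating ntPET with endorphin-sensitive tracers and extending lp-ntPET to the opioid system. Aims 2 and 3 name timing as well as location. Read together, these make voxelwise opioid analysis, and some of it off the HRRT, a live possibility with no written threshold.

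The factual part stands: the document has no second cluster size and no rule for deriving one. Two parts do not. The analyst is not forced to reuse 17 or choose after the fact, because the size can be set for the new setting before any challenge map is opened. The Data Processing text also cannot serve both as evidence that lp-ntPET is unlimited by scanner and as HRRT-only text. As written, its pipeline is HRRT-only. The conflict with the scanner list therefore looks like a drafting mismatch: acquisition options that the processing text does not reflect.

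**Conclusion.** No change to the plan follows. This is an unwritten detail, not a stated rule that gives a wrong answer. The under-1-in-10 claim is confined to the conditions beside it, and nothing in the document extends it to PET-CT, NX-CT or the two-scan opioid data. The size of any effect is unknown in both amount and direction. At most 60 opioid challenge scans are in question, under the group-total reading of n=20, plus whatever unstated share of raclopride scans is done off the HRRT.

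The conclusion assumes ordinary good practice: a cluster test used outside the named conditions is calibrated to the same target before challenge maps are viewed, or those maps are reported as exploratory with no error rate attached. It would not hold if a report quoted the under-1-in-10 rate for a PET-CT or NX-CT map on the strength of the HRRT figure alone.
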